### **6.12.2. Dose-Limiting Toxicities and DLT-Equivalent Toxicities**

Definitions of DLTs and DLT-equivalent toxicities (DETs) are provided in Section 7.2.2.2 of Protocol JZEA.

Dose-limiting toxicities will be summarized and listed for the DLT-evaluable population (defined in Section 7.6.1 of Protocol JZEA), and DETs will be listed and summarized for the safety population.

### **6.12.3. Adverse Events**

A listing of all adverse events (AEs) by patient will be presented. This listing will include patient number, AE (reported term and preferred term [PT]), event start and end dates, Common Terminology Criteria for Adverse Events (CTCAE) grade, relationship to study drug/procedure, seriousness, and outcome. A listing of serious adverse events (SAEs) will be produced using a similar format.

An overall summary will be provided for AEs. The summary will provide counts for all AEs and AEs related to study treatment. Specifically, the number and percent of evaluable patients will be summarized by treatment for each category below:

- patients with at least one treatment-emergent adverse event (TEAE)
- patients with at least one Grade 3 or higher TEAE
- patients with at least one SAE
- patients who discontinued due to AE
- patients who discontinued due to SAE
- patients who died due to AE on study treatment
- patients who died due to AE within 30 days of discontinuation from study treatment

The following summaries will also be produced:

- summary of all preexisting conditions
- summary of TEAEs by PT (any grade and Grade  $\geq 3$ )
- summary of TEAEs by system organ class (SOC) and PT (any grade and Grade  $\geq 3$ )
- summary of TEAEs by SOC and PT and maximum grade (1-5)

- summary of treatment-emergent SAEs by SOC and PT (any grade and Grade  $\geq 3$ )
- summary of AEs as reason for study treatment discontinuation by SOC and PT
- summary of TEAEs leading to dose omissions, reductions, and hospitalization

In addition, immune-related adverse events (irAEs) may be summarized. A list of what is considered an irAE will be defined in a separate document.

#### **6.12.4. Deaths**

All deaths recorded in this study will be included as part of the complete AE listing, where appropriate, and listed separately. A summary of deaths may be presented for all patients on therapy if the number of events is sufficient for this to be deemed useful.

#### **6.12.5. Clinical Laboratory Evaluation**

All laboratory results will be reviewed using Spotfire® to assess changes over time and differences between cohort/dose levels. Key findings will be summarized in tables and/or illustrated graphically using line plots over time or box plots, for example.

Any abnormal results of clinical laboratory tests will be listed for all patients on therapy and, where appropriate, the calculated CTCAE grades using CTCAE version 4.0 (or higher) will be given. Calculated CTCAE grades will also be summarized by cohort/dose level for laboratory parameters where CTCAE grades are available. A shift table of baseline grade by maximum postbaseline grade will be produced.

#### **6.12.6. Vital Signs and Other Physical Findings**

All vital sign results will be reviewed using Spotfire to assess changes over time and differences between cohorts/dose levels. Key findings will be summarized in tables and/or illustrated graphically using line plots over time or box plots, for example.

Any significant physical examination findings and results will be listed.

#### **6.12.7. Electrocardiograms**

Any abnormal electrocardiogram data based on local testing will be listed and summarized for the safety population. Further exploratory analyses may be conducted as warranted.

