#### 9.4.1.1. Electrocardiograms

Perform ECGs as shown in [Appendix 4](#). Triplicate ECGs will be collected in Study JZEA at indicated time points in [Appendix 4](#). During posttreatment follow-up period, single ECGs are collected. ECGs should be recorded according to the study-specific recommendations included in the ECG manual.

ECG recording and vital sign measurements should occur prior to any blood draws scheduled at the same time point. Participants must be supine for approximately 5 to 10 minutes before ECG collection and remain supine but awake during ECG collection.

ECGs will be initially interpreted by a qualified physician at the site (the investigator or qualified designee) as soon after the time of ECG collection as possible (ideally while the patient is still present) to determine whether the patient meets entry criteria and for immediate patient management.

If a clinically significant quantitative or qualitative change from baseline is identified after enrollment, the investigator will assess the patient for symptoms (for example, palpitations, near-syncope, or syncope) and to determine if the patient can continue in the study. The investigator or qualified designee is responsible for determining if any change in patient management is needed and must document his/her review of the ECG printed at the time of evaluation.

Any clinically significant findings that result in a diagnosis and that occur after the patient receives the first dose of study treatment should be reported to Lilly or its designee as an AE via eCRF.

All digital ECGs will be electronically transmitted to a designated central ECG laboratory. The central ECG laboratory will perform a basic quality control check (for example, demographics and study details) and store the ECGs in a database. At a future time, the stored ECG data may be overread at the central ECG laboratory for further evaluation of machine-read measurements or to meet regulatory requirements.

The machine-read ECG intervals and heart rate may be used for data analysis and report writing purposes unless a central ECG laboratory cardiologist overread of the ECGs is conducted prior to completion of the final study report (in which case the overread data would be used).

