For each set of replicates, the cardiologist will determine the R-R and QT intervals and heart rate on the ECGs. These data are not routinely reported back to the investigative site. However, any clinically significant finding that was not present on the fully overread ECG will be reported to the investigator and to Lilly. All data from the overreads will be placed in the Lilly database for analytical and study report purposes.

The investigator's (or qualified designee's) ECG interpretation will be used for decisions about study entry and immediate patient management will be based on the investigator's or qualified designee's ECG interpretation. Data analysis will be based on ECG interpretations performed by the cardiologist at the central ECG laboratory.

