### 10.3. Statistical Analyses

Statistical analysis of this study will be the responsibility of Lilly or its designee.

Unless otherwise stated, all confidence interval (CIs) will be given at a 2-sided 95% level.

Any change to the data analysis methods described in the protocol will require an amendment only if it changes a principal feature of the protocol. Any other change to the data analysis methods described in the protocol, and the justification for making the change, will be described in the Statistical Analysis Plan (SAP) and clinical study report (CSR). Additional exploratory analyses of the data will be conducted as deemed appropriate.

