#### 10.3.1. Safety Analyses

All patients who receive any quantity of LY3434172 will be evaluated for safety and toxicity. Severity grades will be assigned by the investigator using CTCAE Version 5.0.

Safety analyses will include summaries of the following:

- DLTs: the number of patients who experience any DLTs during Cycle 1 will be summarized by cohort by treatment arm
- DLT-equivalent: the number of patients who experience any AE that qualifies as a DLT during any period of study will be summarized by the first dose by treatment arm and by tumor type
- AEs, including severity and possible relationship to study drug
- AEs by Medical Dictionary for Regulatory Activities system organ class (SOC) by decreasing frequency of Preferred Term within an SOC
- laboratory and non-laboratory AEs by CTCAE Version 5.0 term, maximum CTCAE grade, and CTCAE Grade 3 and above (regardless of causality and at least possibly related to study treatment)
- changes in vital signs and ECGs

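### SAP 6.12.7 commits only to ECGs abnormal on local testing and does not implement the protocol's summary of ECG changes from machine-read or overread data

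*SAP*

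**What the plan says.** **Protocol.** Section 10.3.1 lists "changes in vital signs and ECGs" among the summaries that the safety analyses will include. Section 9.4.1.1 deals with the data source in two places. The first reads: "The machine-read ECG intervals and heart rate may be used for data analysis and report writing purposes". It adds an exception: if a central cardiologist overreads the ECGs before the final report is complete, the overread values replace the machine values. The second closes the section without any condition: "Data analysis will be based on ECG interpretations performed by the cardiologist at the central ECG laboratory". For the investigator's reading the section says: "ECG interpretation will be used for decisions about study entry and immediate patient management". Appendix 4 schedules two to three triplicate sets at screening and again before the first dose, then post-dose triplicates up to Cycle 3 Day 1.

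**SAP.** Section 6.12.7 has two sentences. The first is "Any abnormal electrocardiogram data based on local testing will be listed and summarized for the safety population". The second is "Further exploratory analyses may be conducted as warranted". No other SAP section plans an ECG analysis. The neighbouring Section 6.12.6, on vital signs, says: "All vital sign results will be reviewed using Spotfire to assess changes over time and differences between cohorts/dose levels". Table JZEA.6.1 sets a general baseline (the last value reported before the first dose, unless specified otherwise) and specifies nothing different for ECGs.

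**The concern.** One protocol bullet pairs vital signs and ECGs. The SAP carries the vital-sign half into a review of change over time and by cohort, but not the ECG half. A listing and summary of abnormal tracings is not a summary of change: a cohort whose QT lengthens while every patient stays within normal limits would contribute nothing to it.

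The source differs as well. The protocol sends analysis to machine-read or centrally overread values, while the SAP names local testing without defining it. Protocol 10.3 asks that a change of analysis method which needs no amendment be described and justified in the SAP and the study report. The SAP does neither.

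Safety is the primary objective of this first-in-human study, and the replicate ECG schedule is dense enough to give quantitative interval data. As written, the SAP commits to no quantitative use of them.

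**Working it through.** The documents give no figure to reproduce here, so the check is a comparison of text plus two small counts.

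**1. Commitment against implementation**

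| Item | Protocol | SAP |
|---|---|---|
| Vital-sign change | To be summarised (10.3.1) | All results reviewed for change over time and between cohorts (6.12.6) |
| ECG change | To be summarised (10.3.1) | Not committed; optional exploratory work only (6.12.7) |
| ECG source | Machine-read, or overread if done (9.4.1.1) | Local testing, undefined (6.12.7) |
| Reason for difference | Required in SAP and study report (10.3) | None given |

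Timing does not explain the difference. The SAP was approved in April 2019, before protocol amendment (b) was approved in November and December 2019, but the amendment summary lists no change to 9.4.1.1 or 10.3.1.

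**2. Data affected** (Appendix 4, patient treated through Cycle 3 Day 1)

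- Q2W post-dose triplicates: Cycle 1 Day 1 at 1 h and 3 h; Cycle 1 Day 2 at 24 h; and 1 h post-dose on Cycle 1 Day 15, Cycle 2 Day 1, Cycle 2 Day 15 and Cycle 3 Day 1. That is 7 time points × 3 = 21 tracings.
- Q3W: Cycle 1 Day 1 at 1 h and 3 h; Cycle 1 Day 2 at 24 h; and 1 h post-dose on Cycle 2 Day 1 and Cycle 3 Day 1. That is 5 × 3 = 15 tracings.
- Pre-dose on Cycle 1 Day 1: (2 to 3 sets) × 3 = 6 to 9 tracings.

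**3. Secondary point: combining the pre-dose tracings**

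The general baseline rule could select the last tracing, the mean of the last triplicate, or the mean of all 6 to 9. To illustrate the difference, take one patient's change as a post-dose triplicate mean minus baseline. Let m be the number of baseline tracings averaged and t the between-occasion variance divided by the tracing variance. In units of the tracing SD,

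SD of change = √(2t + 1/3 + 1/m).

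The documents give no value of t; 0 and 1 are assumed.

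| | m = 1 | m = 3 | m = 6 | m = 9 |
|---|---|---|---|---|
| t = 0 | 1.155 | 0.816 | 0.707 | 0.667 |
| t = 1 | 1.826 | 1.633 | 1.581 | 1.563 |

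Ratios to the mean of all pre-dose tracings (m = 6, then m = 9):

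- Last single tracing: 1.63 and 1.73 at t = 0; 1.15 and 1.17 at t = 1.
- Last triplicate: 1.15 and 1.22 at t = 0; 1.03 and 1.04 at t = 1.

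These are not bounds. A larger t brings every ratio closer to 1, and the formula has no term for variation between sets taken about 15 minutes apart.

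**The case against.** The case for leaving Section 6.12.7 alone has real content.

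- **The protocol's source is largely settled.** Section 9.4.1.1 already says overread values if an overread is done, otherwise machine values. Only its closing sentence is unconditional. This stands: it is a wording conflict, and a reader should not infer that the protocol leaves the source open.
- **Local testing need not mean the investigator's opinion.** It could cover intervals printed by the site's machine. That is possible, so the SAP cannot be said to rely on the investigator's reading. But the term is undefined, and the mismatch with 9.4.1.1 remains.
- **Serious ECG events are not lost.** A reader might infer that clinically important QT events would go unreported. The documents do not support that. Protocol 9.4.1.1 requires clinically significant findings that lead to a diagnosis to be reported as adverse events, and SAP 6.12.3 summarises treatment-emergent events by grade, system organ class and preferred term.
- **Sponsor standards may supply the rest.** SAP 6.2 uses standard tables and derivations where suitable ones exist, and these may cover replicates. They are not in the documents, and SAP 6.2 allows derivations to be updated at analysis, so this softens the baseline point without closing it.
- **The exploratory sentence permits a change summary.** It does, so the SAP has not withdrawn the protocol's commitment. Permission is still not the commitment in Protocol 10.3.1.
- **The SD ratios say little about the main point.** Agreed. They concern only the choice of baseline for one patient, under an assumed error structure.

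**Conclusion.** The mismatch holds. SAP 6.12.7 commits to a different and undefined source, leaves out a safety summary that the protocol says will be included, and gives no reason. That is more than missing detail, because a programmer who follows the SAP would not produce the protocol's analysis.

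Its reach is limited. What could go unseen is a subclinical shift in QT or corrected QT by cohort or time point. Pulse is covered by SAP 6.12.6. The monkey study showed heart-rate increases but no QTc change (Protocol 3.2). No dose-escalation rule depends on an ECG change summary, and ECGs are not named in the open-ended list of primary safety endpoints. Severity is therefore minor to moderate.

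The conclusion rests on the text alone and on no assumed variance. The baseline ratios, from 1.63–1.73 down to 1.03–1.04 depending on the assumed t and the baseline chosen, illustrate only the secondary point about combining replicates. They should not be read as a range for the effect of the mismatch.

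**What to change.** 1. **SAP 6.12.7.** Add summaries of change from baseline in ECG heart rate and intervals, including a corrected QT, by cohort and scheduled time point. QTcF is one natural choice because exclusion criterion 14 already uses it; Protocol 10.3.1 does not require that particular correction. Name the source with the order already in Protocol 9.4.1.1: overread values if an overread is done before the final report, otherwise machine-read values. Keep the listing and summary of local abnormalities, and define local testing.
2. **Protocol 9.4.1.1.** Align the unconditional closing sentence with that order.
3. **Secondary clarification in the SAP.** State that the replicate mean is used where triplicates are taken and the single value where one ECG is scheduled. Define ECG baseline as the mean of the Cycle 1 Day 1 pre-dose replicates, or of the screening replicates if those are missing.

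**Cost.** One standard table set, a paragraph in the SAP and one sentence in the protocol. The ECGs are already collected and stored centrally. No new overread is needed unless the sponsor keeps the firm closing sentence of 9.4.1.1, in which case the overread is the added cost.

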### **6.13. Efficacy Analyses**

All efficacy analyses will be performed on the safety population. This study is not designed to perform hypothesis testing on efficacy; however, all efficacy data will be listed and summarized.

Response Evaluation Criteria in Solid Tumors (RECIST) version 1.1 (Eisenhauer et al. 2009) will be applied as the primary criteria for assessment of tumor response. Local tumor imaging (investigator assessment with site radiological reading) will be used.

Two sets of analyses will be provided, with 1 set based on RECIST version 1.1 and the other set based on RECIST version 1.1 with confirmatory scan for disease progression. The notation “ir”

(immune-related) will be used to denote the analyses based on RECIST version 1.1 with confirmatory scan for disease progression; it does not indicate that any of the assessments based on irRECIST, irRC, or iRECIST will be used in the study or analyses.

### **6.13.1. Tumor Measurement**

Tumor size is the sum of the uni-dimensional measurements for each lesion. Change in tumor size is defined as the percent change in tumor size from the baseline evaluation to the postdose evaluation at each assessment.

Individual changes in the tumor size over time will be presented graphically by waterfall and spider plots within a tumor type.

### **6.13.3. Time to Response**

Time to response (TTR) is the time from the date of first study treatment until the first evidence of a confirmed CR or PR. If a patient did not experience a confirmed CR or PR, the TTR will be censored at the treatment starting date.

Time to response will be estimated using the Kaplan-Meier (KM) method (Kaplan and Meier 1958) and summary statistics including median and 95% CI will be presented.

### 6.13.4. Progression-Free Survival

Progression-free survival is defined as the time from the date of first dose until the date of the first observed radiographic documentation of progression or death due to any cause, whichever is earlier.

Table JZEA.6.2 lists rules for determining date of progression or censor for PFS.

**Table JZEA.6.2. Rules for Determining Date of Progression or Censor for Progression-Free Survival**

Situation	Event/Censor	Date of Event or Censor
Tumor progression or death	Event	Earliest date of PD or death
No tumor progression and no death	Censored	Date of last adequate radiological assessment or date of first dose (whichever is later)
unless		
No baseline radiological tumor assessment available	Censored	Date of first dose
No adequate postbaseline radiological tumor assessment available  and death reported after 2 consecutively missed tumor assessment intervals following enrollment	Censored	Date of first dose
New anticancer treatment started	Censored	Date of adequate radiological assessment prior to start of new therapy or date of first dose (whichever is later)
Tumor progression or death documented immediately after 2 or more consecutively missed tumor assessment intervals following last adequate radiological tumor assessment or enrollment (whichever is later)	Censored	Date of last adequate radiological assessment or date of first dose (whichever is later)

Abbreviation: PD = partial disease.

**Note:** 1) If there are multiple dates associated with 1 radiological tumor assessment, the assessment date will be set to the first date when the overall response is PD and the last date otherwise; 2) Symptomatic deteriorations (ie, symptomatic progressions, which are not radiologically confirmed) will not be considered as progressions; and 3) A radiological tumor assessment is considered adequate if its response is among CR, PR, SD, or PD.

Progression-free survival will be estimated using the KM method. Median PFS and 95% CI as well as PFS rates (and 95% CI) at 12, 18, and 24 weeks will be presented.

### **6.13.6. Immuno-Related Efficacy Analysis Variables**

Study JZEA will use RECIST version 1.1 with confirmatory scan for disease progression. Detailed application of RECIST version 1.1 with confirmatory scan for PD can be found in Section 9.1.1.2 of Protocol JZEA.

**Immune-related objective response rate (irORR)** is defined as the proportion of treated patients achieving a BOR of CR or PR per RECIST version 1.1 with confirmatory scan for PD—particularly, the BOR by RECIST version 1.1 with confirmatory scan for PD closely related to confirmed response by RECIST. Immune-related objective response rate further captures responses after unconfirmed PD and does not require confirmation. For example:

- If the best response by RECIST version 1.1 is CR, then the best response by RECIST version 1.1 with confirmatory scan for PD is CR.
- If the best response by RECIST version 1.1 is PR, SD, or PD, the best response by RECIST version 1.1 with confirmatory scan for PD is the best response over the initial assessment (prior to PD by RECIST) and the confirmation stage.

Overall, the best response by RECIST version 1.1 with confirmatory scan for PD should be the same or better than the best response by RECIST criteria. In addition, patients who do not have any postbaseline tumor response assessments for any reason are considered NE and will be included in the denominator when calculating the response rate.

**Immune-related disease control rate (irDCR)** is defined as the number of patients with immune-related stable disease (irSD), immune-related complete response (irCR), or immune-related partial response (irPR) divided by the number of enrolled patients who have received any quantity of study treatment.

**Immune-related time to response (irTTR)** is the time from the date of first study treatment until the first documented irCR or irPR.

**Immune-related PFS (irPFS):** The date from the treatment start date to the time of PD assessed by RECIST version 1.1 with confirmatory scan for PD.

- If the initial PD is confirmed, then the date of immune-related partial disease (irPD) is the initial PD date by RECIST version 1.1.
- If the initial PD is unconfirmed, then the date of irPD is the date of second PD.

**Immune-related duration of response (irDoR):** The irDoR is defined from the date of first documented irCR or irPR (responder) to the date of irPD or the date of death due to any cause, whichever is earlier.

In addition, the best response after initial PD may be listed. Other efficacy analysis based on irRECIST may be performed for exploratory analysis.

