### **10.3.2. *Efficacy Analyses***

The study was not designed to make an efficacy assessment. However, any tumor response data will be tabulated, where appropriate, for all patients in the enrolled/safety analysis set.

The efficacy endpoints are listed and defined as follows:

**Objective response rate (ORR)** is the proportion of enrolled patients who have received any amount of either study drug, have at least one postbaseline tumor image, and achieved a best overall response (BOR) of confirmed CR or PR.

**Duration of response (DoR)** is defined only for responders (patients with a confirmed CR or PR). It is measured from the date of first evidence of a confirmed CR or PR to the date of the first observed radiographically documented PD, or the date of death due to any cause, whichever is earlier. If a responder is not known to have died or have objective progression as of the data inclusion cutoff date, DoR will be censored at the date of the last complete objective progression-free disease assessment.

**Time-to-response (TTR)** is the time from the date of first study treatment until the first evidence of a confirmed CR or PR.

**Disease control rate (DCR)** is the proportion of enrolled patients who have a BOR of confirmed CR, confirmed PR, or stable disease (SD).

**Progression-free survival** is defined as the time from the date of first study treatment until the date of the first observed radiographically documented PD or death due to any cause, whichever is earlier. The censoring is taken in the following order:

- If a patient does not have a complete baseline disease assessment, then the PFS time will be censored at the enrollment date, regardless of whether or not objectively determined disease progression or death has been observed for the patient; otherwise,

- if a patient is not known to have died or have objective progression as of the data inclusion cutoff date for the analysis, the PFS time will be censored at the last complete objective progression-free disease assessment date.

**Overall survival**, an exploratory objective, is determined from the date of first study treatment until death due to any cause. If the patient is not known to have died at the data inclusion cutoff date for the analysis (or is lost to follow-up), OS will be censored on the last date the patient was known to be alive. This endpoint will be followed up for 12 months after the last patient has entered treatment.

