The objective response rate, TTR, DCR, DoR, and PFS will be assessed based on RECIST v1.1 (Eisenhauer et al. 2009) and RECIST v1.1 with confirmatory scan for disease progression (Section 9.1.1).

The estimate of ORR and DCR, and the corresponding CI, will be provided by dose-level (cohort) according to RECIST v1.1 and RECIST v1.1 with confirmatory scan for disease progression (Section 9.1.1). Time-to-event variables, such as TTR, DoR, PFS (as an exploratory objective), and OS (as an exploratory objective), will be summarized by Kaplan and Meier (1958) method by dose-level (cohort) where appropriate. Presentations of antitumor activity may include patients enrolled in the dose-level (cohort) with the same tumor type and dosing scheme. Individual changes in the tumor burden over time will be presented graphically within a tumor type. Subgroup analysis of interest will be further defined in the SAP.

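### SAP 6.13.6 waives response confirmation for the immune-related endpoints, against Protocol 10.3.2, without marking the departure or giving a reason

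*SAP*

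**What the plan says.** **Protocol.** Section 10.3.2 counts a patient towards ORR if the patient has "achieved a best overall response (BOR) of confirmed CR or PR". DoR is restricted to confirmed responders: "It is measured from the date of first evidence of a confirmed CR or PR". TTR likewise runs to the first evidence of a confirmed response. The same section then says that these endpoints, with DCR and PFS, are assessed under two criteria, and that the ORR and DCR estimates "will be provided by dose-level (cohort) according to RECIST v1.1 and RECIST v1.1 with confirmatory scan for disease progression". It gives no separate definition of a responder for the second criterion. Section 9.1 calls for CR and PR to be confirmed by repeat imaging at least 4 weeks later and makes no exception. Section 10.3 says that a change in analysis method that needs no amendment, together with its justification, is to be described in the SAP and the study report.

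**SAP.** Sections 6.13.2, 6.13.3 and 6.13.5 keep confirmation for the RECIST 1.1 set. Section 6.13.6 does not keep it for the ir set: "Immune-related objective response rate further captures responses after unconfirmed PD and does not require confirmation". There irTTR runs "until the first documented irCR or irPR", and irDoR starts at that same point. The same section describes the ir best response as "closely related to confirmed response by RECIST". For patients whose RECIST 1.1 best response is PR, SD or PD, it says that the ir best response "is the best response over the initial assessment (prior to PD by RECIST) and the confirmation stage".

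**The concern.** A reader who sets irORR beside ORR will naturally take the gap as the yield of allowing for an unconfirmed progression. Under SAP 6.13.6 the gap also contains responses seen on one scan only, which Protocol 10.3.2 would not count. irTTR and irDoR would then describe a different kind of responder from TTR and DoR. The scope of the waiver is also open, so two programmers could derive different ir best responses from the same data. Results are reported by dose level, where one patient moves the rate a good deal.

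**Working it through.** The plan states no figure to reproduce, so the check is a comparison of texts followed by an illustration.

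**1. Does the protocol's second criterion waive response confirmation?** Table JZEA.11 compares the criteria on two points, new lesions and confirmation of PD. Section 9.1.1.2 adds the PD rule on top of standard RECIST 1.1. Neither relaxes confirmation of CR or PR. Reading the 10.3.2 definitions together with the statement that they apply under both criteria, confirmation carries over.

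**2. What enters irORR beyond ORR?** In the SAP both rates use all treated patients, including those not evaluable, so only the numerators differ. Define:
- A = patients with a confirmed response first seen after an unconfirmed PD
- B = patients whose only response is unconfirmed and follows an unconfirmed PD
- C = patients whose only response is unconfirmed and does not follow an unconfirmed PD (for example one PR scan, then confirmed PD)

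| Reading of SAP 6.13.6 | irORR numerator minus ORR numerator |
|---|---|
| Waiver covers only responses after an unconfirmed PD | A + B |
| Waiver covers all ir responses | A + B + C |
| Confirmation required, as in Protocol 10.3.2 | A |

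Only A is the effect of PD handling. B enters on either reading and C only on the broad one. The phrase "closely related to confirmed response by RECIST" favours the narrow reading but does not settle it.

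**3. Do the start dates move?** SAP 6.13.5 starts DoR at the initial response scan, not at the confirming scan. For a response that is later confirmed, the first documented response and the first evidence of a confirmed response are therefore the same date. What changes in irTTR and irDoR is who is in the analysis.

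**4. Illustration of size.** The documents give no rate for B or C. The cohort sizes below are assumptions built from Protocol 5.1.1 (12 to 15 expansion patients in total over two levels) and 5.2 (minimum of three per cohort):
- unexpanded cohort: n = 3
- expanded level, low: 12/2 + 3 = 9
- expanded level, high: 15 split as 7 and 8, so 8 + 3 = 11

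One extra response adds 100/n percentage points. Intervals are exact (Clopper-Pearson) 95%, the type that SAP 6.13.2 names.

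| n | Points per response | Before | After one extra response |
|---|---|---|---|
| 3 | 33.3 | 0/3 = 0% (0 to 70.8) | 1/3 = 33.3% (0.8 to 90.6) |
| 9 | 11.1 | 1/9 = 11.1% (0.3 to 48.2) | 2/9 = 22.2% (2.8 to 60.0) |
| 11 | 9.1 | 1/11 = 9.1% (0.2 to 41.3) | 2/11 = 18.2% (2.3 to 51.8) |

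The intervals overlap heavily. The table shows how far a point estimate can move, not an expected bias.

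**The case against.** The strongest reply is that a broader ir set is a legitimate exploratory choice. Protocol 9.1.1.1 says that the variant is meant to capture delayed responses and responses after progression, and the glossary in Protocol Appendix 1 defines ORR and DoR without the word confirmed. The SAP states its rule openly, and all efficacy data are to be listed. Part of this stands: an unconfirmed irORR would be acceptable if its scope and reason were given. But Protocol 9.1 points to 10.3.2 for the endpoint definitions, and the SAP itself follows 10.3.2 everywhere except in 6.13.6. The summary of amendment (b), which is later than the SAP, lists no change to 10.3.2, so that amendment does not explain the difference.

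Some stronger readings are tempting, and the documents do not support them:
- *The SAP conceals the rule.* It states the rule. What is missing is its identification as a departure and the justification.
- *irTTR and irDoR start on the wrong date.* For later-confirmed responses no date changes.
- *The protocol requires the two sets to differ only in PD handling.* No sentence says so. It is an inference from Table JZEA.11, 9.1.1.2 and 10.3.2, though a reasonable one.
- *The recommended dose or the biomarker trigger is affected.* SAP 5.1 rests the recommended dose on DLTs and PK/pharmacodynamic data. The 10% trigger in SAP 6.17 refers to ORR, not irORR.

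**Conclusion.** The mismatch is real. As written, SAP 6.13.6 lets single-scan responses into irORR, irTTR and irDoR that the Protocol 10.3.2 definitions exclude. It gives no reason and leaves the scope of the waiver unclear. This rests on carrying the confirmed-response definitions of 10.3.2 into the second criterion, for which the protocol offers no alternative.

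The size is unknown. Under the assumed cohort sizes, each extra unconfirmed response is worth 9.1 to 33.3 percentage points at a dose level. The consequence is limited: these endpoints are secondary and descriptive, SAP 6.6 plans no hypothesis test, and Protocol 10.3.2 says that the study was not designed to assess efficacy. Confirmed RECIST 1.1 ORR is still reported with an exact interval. The point should be corrected, but it does not threaten the primary objective.

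**What to change.** **Preferred.** In SAP 6.13.6, define irORR, irTTR, irDoR and the response component of irDCR by CR or PR confirmed at least 4 weeks later, with the same assessment limits as SAP 6.13.2. Change only the PD cut-off, from first RECIST PD to irPD, so that a response after an unconfirmed PD counts if it is confirmed.

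**If the unconfirmed irORR is kept.** State which responses the waiver covers and why, as Protocol 10.3 requires, and report the confirmed version alongside.

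**In either case.** Make the listing of best response after initial PD, now optional at the end of 6.13.6, a firm one, and flag unconfirmed responses in it.

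**Cost.** SAP wording, a little more programming and one listing, with no scans beyond those Protocol 9.1 already calls for. irORR may come out slightly lower.

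**Separate, and not needed for this fix.** Define the confirmation stage, and reconcile the timing of the PD confirmatory scan. Table JZEA.11 and 9.1.1.2 put it at 4 to 6 weeks. Section 9.1 puts a confirmatory assessment at the next routine scan; that bullet does not name PD but cross-refers to 9.1.1. With first PD at the first on-study scan, ignoring visit windows, the Q2W cohorts give weeks 8 + 4 to 8 + 6 = 12 to 14 against week 8 + 8 = 16. The Q3W cohorts give weeks 6 + 4 to 6 + 6 = 10 to 12 against week 6 + 6 = 12, which is compatible. The discrepancy therefore lies mainly in the Q2W cohorts.
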